4. SELECTION OF STUDY POPULATION

Patients ≥ 18 years with severe Sjögren's dry eye will be included. A total of 100 patients will be enrolled. The safety and efficacy of cenergermin ophthalmic solution will be investigated in these patients.

4.1. INCLUSION CRITERIA

To be eligible for inclusion into this study, each patient must fulfil the following inclusion criteria:

1. Male or female aged ≥ 18 years
2. Patients with a confirmed diagnosis of Sjögren's syndrome or other autoimmune disease known to induce Sjögren's Dry Eye Disease (DED).
3. Patients with severe Sjögren's dry eye disease characterized by the following clinical features:
 - a. Corneal and/or conjunctival staining with fluorescein using National Eye Institute (NEI) grading system ≥ 3
 - b. SANDE questionnaire >25 mm
 - c. Schirmer test I (without anaesthesia) $\geq 2 \leq 5$ mm/5min
4. The same eye (eligible eye) must fulfill all the above criteria
5. Patients diagnosed with severe Sjögren's dry eye disease at least 3 months before enrolment (current use or recommended use of artificial tears for the treatment of Sjögren's related Dry Eye)
6. Best corrected distance visual acuity (BCDVA) score of ≥ 0.1 decimal units (20/200 Snellen value) in each eye at the time of study enrolment
7. If a female of childbearing potential, have a negative urine pregnancy test and use a highly effective method to avoid pregnancy for the duration of the trial and 30 days after the study treatment period. Males of reproductive potential should use effective contraception during treatment and 30 days after the study treatment period.
8. Only patients who satisfy all Informed Consent requirements may be included in the study. The patient and/or his/her legal representative must read, sign and date the Informed Consent document before any study-related procedures are performed. The Informed Consent form signed by patients and/or legal representative must have been approved by the IRB/IEC for the current study
9. Patients must have the ability and willingness to comply with study procedures

EXCLUSION CRITERIA

1. Inability to speak and understand the local language sufficiently to understand the nature of the study, to provide written informed consent, and to allow the completion of all study assessments
2. Evidence of an active ocular infection, in either eye
3. Presence of any other ocular disorder or condition requiring topical medication during the entire duration of study in either eye

4. History of severe systemic allergy or of ocular allergy (including seasonal conjunctivitis) or chronic conjunctivitis and/or keratitis other than dry eye
5. Intraocular inflammation defined as Tyndall score >0
6. History of malignancy in the last 5 years
7. Systemic disease not stabilized within 1 month before Screening Visit (e.g. diabetes with glycemia out of range, thyroid malfunction) or judged by the investigator to be incompatible with the study (e.g. current systemic infections) or with a condition incompatible with the frequent assessment required by the study
8. Patient had a serious adverse reaction or significant hypersensitivity to any drug or chemically related compounds or had a clinically significant allergy to drugs, foods, amide local anesthetics or other materials including commercial artificial tears (in the opinion of the investigator)
9. Females of childbearing potential (those who are not surgically sterilized or post-menopausal for at least 1 year) are excluded from participation in the study if they meet any one of the following conditions:
 - a. are currently pregnant or,
 - b. have a positive result at the urine pregnancy test (Baseline/Day 1) or,
 - c. intend to become pregnant during the study treatment period or,
 - d. are breast-feeding or,
 - e. are not willing to use highly effective birth control measures, such as: combined (estrogen and progesterone containing) hormonal contraceptives associated with inhibition of ovulation (oral, intravaginal, transdermal), progestogen-only hormonal contraception associated with inhibition of ovulation (oral, implantable, injectable), intrauterine device (IUD), intrauterine hormone-releasing system (IUS), bilateral tubal occlusion, vasectomised partner, sexual abstinence during the entire course of and 30 days after the study treatment period.
10. Any concurrent medical condition, that in the judgment of the PI, might interfere with the conduct of the study, confound the interpretation of the study results, or endanger the patient's well-being
11. Use of topical cyclosporine, , or topical ophthalmic treatments of the same class, within 14 days of screening visit (day -8)
12. Use of topical corticosteroids, lifitegrast, autologous serum tears in either eye during the study (previous use not an exclusion criteria but must be discontinued at the screening visit)
13. Contact lenses, True Tear device, moisture goggles, sutureless amniotic membrane or punctum plug use during the study (previous use not an exclusion criteria but must be discontinued at the screening visit)
14. History of drug addiction or alcohol abuse in the last 2 years
15. Any prior ocular surgery (including refractive, palpebral and cataract surgery) if within 90 days before the screening visit

- 16.** Participation in a clinical trial with a new active substance during the past 3 months
- 17.** Participation in another clinical trial study at the same time as the present study.

4.2. ELIGIBLE EYE

Assuming that all the inclusion/exclusion criteria are met in both eyes, the worse eye (eligible eye) will be determined **at the baseline visit using** a stepladder approach, as follows:

1. Schirmer's Test (since this is the primary endpoint)-Worse eye determined as eye with lower Schirmer I score.
2. NEI score (cornea+conjunctival staining) - If Schirmer I score is the same in both eyes, worse eye will be determined by NEI score (cornea+conjunctival staining).

If all of the above are identical, determination of the worse eye will be based on the Investigator's judgement, otherwise **simply use the right eye** as the eligible eye.

4.3. ASSIGNMENT OF PATIENT NUMBER

Each patient who provides written consent to participate in this study will be assigned a unique 5-digit PID number (e.g. 01-001) consisting of a 2-digit study center number followed by the 3-digit screening number assigned sequentially by each study center, from 001 to 100.

4.4. RANDOMIZATION

Eligible patients will be randomized in a 1:1 ratio to either cenegegermin ophthalmic solution 20 mcg/mL TID (~50 patients) or vehicle ophthalmic solution TID (~50patients).

Each randomized patient will be allocated with randomization number, according to the stratified randomization list. Drop outs after randomization will not be replaced.

Randomization will be stratified by site to ensure balanced assignment across treatment groups. The stratified permuted block randomization list will be generated with a computer procedure by an independent statistician not involved in the conduct of the study.

Randomization will be performed through IRS. Each Patient Kit number will be randomly associated with a treatment group. The randomization list will be provided to the facility responsible for IMP packaging/labelling for the purpose of IMP preparation. Each randomized patient will be allocated with randomization number according to the stratified randomization list. Dropouts after randomization will not be replaced

The enrollment of patients will be scheduled in order to assure an inclusion of approximately 100 patients to ensure at least 90 patients assuming up to 10% dropout rate.

4.5. MASKING

The identity of the treatments will remain unknown to the patient, Investigator, site staff and Sponsor's clinical research personnel until the completion of the study (after full data base lock) except in case of specific events that will require unmasking of the patient.

The vials containing cenegegermin (20 mcg/mL) or vehicle will be identical in appearance, and the contents of the vials will be indistinguishable. All staff directly involved in the analysis of study results will remain masked to treatment assignments while the study is in progress.

A list of sequential kit numbers will be generated by an independent statistician not involved in the conduct of the study. Each kit number will be randomly associated with a treatment group. Patients will be assigned to treatment in numerical order. A tear-off label from the kit box, with the kit number, will be attached to the investigational product dispensing log.

The investigator will be provided with a protected access to the randomization list so only in case of a medical emergency the Investigator can open the treatment allocation for a specific patient.

Also Dompé's Pharmacovigilance contact person will be provided with a protected access to randomization list , so if required by the Pharmacovigilance activities the Pharmacovigilance contact person can open the treatment allocation for a specific Patient.

In the event of a medical emergency where the knowledge of patient treatment is required to provide the patient with appropriate care, Investigators will have the possibility to unmask the treatment assignment for a specific patient. The Investigators are encouraged to contact the CRO staff before becoming unmasked if there is sufficient time.

If the Investigator becomes unmasked for any reason, this information will be recorded on source data and in the eCRF of the study, specifying the date and the reason.

Unmasking events will be recorded and reported in the final study report.

5. STUDY MEDICATION

5.1. DESCRIPTION OF PRODUCT

5.1.1. Presentation of Non Investigational Medicinal Product (NIMP)

TEST PRODUCT

NIMP

Blink® Tears or equivalent preservative-free artificial tears

Pharmaceutical form

Lubricating Eye Drops

Administration

One drop of Blink® Tears or equivalent will be instilled in both eyes during the screening week, only if strictly needed by the patient. The patient must document in the patient's diary the n° of additional drops administered for each eye.

One drop of Blink® Tears or equivalent will be instilled in both eyes during the 4 weeks of masked treatment, only if strictly needed by the patient. The patient must document in the patient's diary the n° of additional drops administered for each eye.

One drop of Blink® Tears or equivalent will be instilled in both eye TID (morning, afternoon and evening) during the initially 8 weeks of follow up. The patient, only if strictly needed, can administer additional drops and must document in the patient's diary the n° of additional drops administered for each eye.

Administration route

Ocular

5.1.2. Presentation of Investigational Medicinal Product

TEST PRODUCT

IMP

Cenegermin (rhNGF
20 mcg/mL) and/or Placebo vehicle (Vehicle vials).

Manufacturer active substance

Dompé Farmaceutici S.p.A., Italy

Manufacturer finished product	Bulk drug product is manufactured by PPD Secondary packaging and labelling is performed by PPD
Pharmaceutical form	Ophthalmic sterile solution
Dose	Test and reference will be instilled in both eyes according to the following scheme: Group 1: one drop of cenegegermin 20 mcg/mL will be instilled in both eyes three times daily (every 6 hours, e.g. 7:00 am, 01:00 pm; 07:00 pm). Group 2: vehicle : one drop of vehicle ophthalmic solution will be instilled in both eyes three times daily (every 6 hours, e.g. 7:00 am, 01:00 pm; 07:00 pm).
Administration route	Ocular

5.2. FORMULATION AND PACKAGING

The Investigator will be provided with a subject monthly box containing 4 weekly boxes of frozen IMP solutions (-20 ± 5°C) that, in-turn, contain 7 daily vials to be stored in refrigerator at 2-8 °C (36° F to 46° F) or at room temperature not exceeding 12 hours. Each vial contains:

- cenegegermin, at concentrations of 20 mcg/mL, and/or
- vehicle (placebo).

Together with the IMP monthly box, the patients will be provided with a sufficient number of pipettes and adapters and wipes to be used for the administration of the IMP.

Pipettes, and adapters and wipes will be provided separately in single sterile packages and may be kept at room temperature.

The vial adapter is a device for safe transfer of drug between vial and pipette. The pipette is used with an adapter consisting of a connecting device with dual connections: one end for the pipette and one end for the vial. The patient will need to:

1. Put the adapter on the top of the vial (after removing the plastic seal) by piercing the septum

2. Put the pipette on adapter inlet
3. Draw the solution contained in the vial with the pipette until this reaches its capacity
4. Remove the pipette and use it as a dropper to administer one drop of IMP into each eye.

5.3. STORAGE AND HANDLING OF IMP

The Pharmacist and/or Investigator will be responsible for receipt, proper storage, and usage of study drug, as well as for the IMP distribution, collection of used and unused vials and final disposal of the remaining IMP.

The investigational product must be stored at -20 ± 5 °C at the investigational sites, in an appropriate locked room accessible only to the pharmacist, the Investigator, or a duly designated person.

A temperature probe and data logger will accompany the drug on shipment. It is essential that the investigational sites will verify the temperature excursion during shipment vs. the acceptable storage conditions, in order to identify potential stability concerns during shipment. These must be immediately communicated to the Sponsor that will decide upon appropriate actions to be taken. The IMP will be stored in a locked place, sheltered from light. The vials will be not shaken since agitation of vials may cause foaming and/or particle formation.

On Day 1 (baseline visit), the study personnel will give to the patient the monthly boxes containing the study medications

Patient should bring the study medication, one monthly box, at home as soon as possible and immediately store it in a freezer at -20 ± 5 °C.

The weekly box must be kept at 2-8°C for 7 days protected from light; the daily vial can be kept at room temperature, before the patient will use the single vial for each instillation (both eyes) as long as 12 hours are not exceeded. Agitation of vials may cause foaming and/or particle formation. Drug preparation and administration instructions will be provided separately to the site and to the patients.

Together with the IMP monthly box, the patient will also receive a separate administration kit of vial adapters (one per vial), pipettes (3 per vial) and disinfectant wipes (3 per vial); some spare samples could be provided to ensure product administration.

IMP ophthalmic solution instruction will be provided to patients.

Patients will use one vial to instill one drop in both eyes (**group 1**: cenegeerin TID; **group 2**: vehicle TID) three times a day (approximately every 6 hours), starting in the morning when they wake up, for a total duration of 4 weeks" .

The contents of each vial are for the daily administration to both eyes only. After the last administration the used vial should be returned to the original medication box and is not to be reused.

Any deviations from the recommended storage conditions should be immediately reported by the pharmacist to the Sponsor and Investigator, and the use of the drug should be suspended until they have given authorization for its continued use. The IMP supplies are to be used only in accordance with this protocol. The Investigator will not use any drug samples for other purposes (e.g., treating patients or deviating from the protocol with regard to dose regimen, duration of treatment, etc.). Under no circumstances will the Investigator give any drug samples to a third party.

5.4. DOSE, ROUTE AND SCHEDULE OF IMP ADMINISTRATION

5.4.1. Administration route

The Administration route is topical ophthalmic application.

5.4.2. Dose regimen

In all patients both eyes will be treated for a period of 4 weeks.

The dosing scheme of the different study groups is summarized below:

Group 1: one drop of cenegegermin 20 mcg/mL will be instilled in both eyes three times daily (every 6 hours, e.g. 7:00 am, 01:00 pm; 07:00 pm).

Group 2: one vehicle drop will be instilled in both eyes three times daily (every 6 hours, e.g. 7:00 am, 01:00 pm; 07:00 pm).

During the 4 weeks of masked treatment only the administration of IMP is allowed. Nevertheless, if strictly needed, the patient can take a preservative free artificial tears (provided by the Sponsor). The use (n° drops/day) of preservative free artificial tears will be clearly documented in a patient's diary and in the eCRF.

Both the patients and the investigator will be masked to the study treatment.

Information about the study drug administration, and comments, will be recorded on the appropriate page of the eCRF.

5.5. ACCOUNTABILITY OF THE IMP

The Pharmacist and/or Investigator will confirm the receipt of the IMP supply in writing by signing and dating standard drug accountability forms.

At the week 4 (end of treatment visit) the patient will return the used or unused study boxes/vials to the Investigator.

The Pharmacist and/or Investigator will keep a cumulative inventory and dispensing records, and will maintain all supplies under adequate security.

An accurate drug disposition record will be kept, specifying the date and amount dispensed to each patient.

Adequate record of receipt and use or loss of drug will be retained. This inventory record must be available for inspection by the Sponsor and regulatory inspection at any time. Copies of this record will be provided to the Sponsor by the CRO throughout the duration of the study.

At the scheduled visit, the patient diary should be reviewed by the Investigator with the patient for completeness. Missing information should not be provided during the diary check but reported as missing.

During the course of the study and until its conclusion, the Investigator will complete the drug accountability forms. Partially used or unused study drug boxes will be verified by the Investigator and within one month after completion of the trial the partially used and unused study medication will be shipped to the Sponsor or will be destroyed after authorization by the Sponsor or by an authorized company according to GCP regulations.

5.6. CONCOMITANT MEDICATION

As a general rule, no ophthalmic medication other than study drug will be given to the patient from the screening day until all of the final study evaluations have been completed, except for preservative free artificial tears provided by the Sponsor.

The preservative free artificial tears will be provided by the Sponsor and can be used according to the following scheme:

- 1) During the 4 weeks of masked treatment, only if strictly needed, the patient will instill one drop in both eyes.
- 2) During the 8 weeks of Follow-up period post-treatment one drop will be instilled in both eyes TID (morning, afternoon and evening).

The use (n° drops/day) of preservative free artificial tears will be clearly documented in the patient's diary and eCRF.

All medications (including over-the-counter drugs, herbal products, vitamins, and antacids) taken within 4 weeks prior to the start of and throughout the study will be clearly documented on the Concomitant Medications eCRF page.

Medication entries should be specific to product name (if a combination drug product) and spelled correctly. The dose, unit, frequency, route of administration, start date, discontinuation date, and indication should also be recorded. For medications administered only one time, the frequency column may reflect "once."

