3.3. OVERALL STUDY DESIGN

This is a 4 week phase III, multicenter, double-masked, vehicle-controlled study to evaluate safety and efficacy of cenegegermin ophthalmic solution at 20 mcg/mL solution versus vehicle, in patients with severe Sjogren's dry eye disease

Patients will be evaluated as per Section 2 "SCHEDULE OF EVALUATIONS".

During the screening (day-8) all procedures for inclusion will be performed. From the day of screening the patients will stop any kind of further treatment, except commercially available preservative free artificial tears provided by Sponsor for a period of 8 days and 10 days as maximum: day -8 until the baseline visit (day 1+2), Figure 1. At the end of the wash out period (day -8 to baseline), patients meeting the entry criteria for this study will be randomized 1:1 and treated for 4 weeks with either cenegegermin ophthalmic solution 20 mcg/mL TID or vehicle TID.

During the 4 weeks of masked treatment only the administration of IMP is allowed. Nevertheless, if strictly needed, the patient can take preservative free artificial tears (provided by the Sponsor). The use (n° drops/day) of preservative free artificial tears will be clearly documented in a patient's diary and in the eCRF.

Eight weeks post treatment with no further topical ocular treatment except commercially available preservative-free artificial tears provided by the Sponsor three times daily will follow the completion of the double-blind treatment. During this follow up period, the patient can administer additional artificial tear eye drops, provided by Sponsor, only if strictly needed, and must document in the patient's diary the number of additional drops administered for each eye.

Patients will then be followed up for efficacy and safety endpoints until week 16 and for safety endpoints until week 24. During the follow up period after week 12 until week 24 other topical treatments will be allowed at discretion of the treating physician. Such treatments will be recorded by the investigators.

Throughout the study, the patient can continue any systemic treatment as required to control their autoimmune disease, and any change in systemic treatments must be recorded by the investigators.

The total duration of the study is 25 weeks including 1 week of screening.

[figure not shown]

Figure 1. Study duration

3.3.1. Rationale for Selection of dose, control group and treatment schedule in the study

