6.1. SCREENING AND RANDOMIZATION VISITS

During the screening visit (day -8) all procedures for will be performed. From the day of screening the patients will stop any kind of further ophthalmic treatment, until all of the final study evaluations have been completed, except preservative free artificial tears (wash out period from day -8 to baseline, Day 1 +2). The wash out period should not be less than 8 days and more than 10 days.

At the end of the screening period, patients meeting the entry criteria for this study will be randomized 1:1 and treated for 4 weeks with either cenegeamin ophthalmic solution 20 mcg/mL TID or vehicle TID.

Slit lamp examination and the fluorescein staining (Corneal and/or Conjunctival staining with Fluorescein) will be performed at different time-points, as specified in the section 2 of “SCHEDULE OF EVALUATIONS” and procedure will be detailed on the informed consent form.

An independent Blinded Reading Center (RC) will also be used to assess the images collected at protocol-specified time points and sent to the RC as specified in the RC procedure manual.

The RC will provide instructions for the slit lamp photography and the fluorescein staining procedures.

	Day	Procedures/Assessments

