6.2. STUDY VISITS AND FOLLOW-UP ASSESSMENTS

After the first two weeks of treatment the patient will undergo a medical assessment during the visit 2 (week 2). Following the completion of the double-blind treatment (visit 3, week 4), patients will be followed up for efficacy until visit 6 (week 16) and safety assessments until visit 7 (week 24). During the follow-up period until

week 12 patients will not use further ophthalmic treatment except preservative free artificial tears, provided by Sponsor, one drop instilled in both eyes three times daily (morning, afternoon and evening). The patient, only if strictly needed, can administer additional drops and must document in the patient's diary the n° of additional drops administered for each eye. After week 12 (visit 5), patients will be followed-up for additional 12 weeks until the end of the study (visit 7, week 24) during which patients can use others artificial tears different from the artificial tears provided by the Sponsor.

Slit lamp examination and the fluorescein staining (Corneal and/or Conjunctival staining with Fluorescein) will be performed at different time-points, as specified in the section 2 of "SCHEDULE OF EVALUATIONS" and procedure will be detailed on the informed consent form.

An independent Blinded Reading Center will also be used to assess the images collected, as described in the previous paragraph.

	Day	Procedures/Assessments
At home	Days 1-14 ±2	
 ➤ Self-administration at home of the IMP, three times daily every 6 h for both eyes (diary) ➤ Recording any new or changes in concomitant medications (diary) ➤ Recording any unusual medical conditions - AE monitoring (diary) ➤ Recording possible use of preservative free artificial tears (diary). 
Data will be recorded by the patient in the patient's diary.

	Day	Procedures/Assessments

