Visit 5 Follow up week 12	Day 84 ± 4	
The following procedures will be performed (the below order is mandatory):
 
 ➤ Ocular examination of both eyes to be performed by the physician investigator: 
 • Assessment by SANDE questionnaire • Assessment by IDEEL questionnaire • Assessment of best corrected distance visual acuity (BCDVA) • External Ocular Examination • Schirmer test I (without anesthesia) • Slit-lamp examination (SLE) to assess the Eyelid - Meibomian glands, Eyelid – Erythema, Eyelid - Edema Lashes, Conjunctiva Erythema, Lens, Iris, Anterior Chamber, Corneal Horizontal Diameter • TFBUT • Ocular surface staining (NEI score - corneal and conjunctival fluoresce instaining) ➤ Concomitant ocular and systemic medications ➤ Frequency of patient's artificial tear use during 4 weeks of FU (to be reported in eCRF). ➤ AE monitoring 
During visit 5, week 12, PI or delegate must check and collect the patient's diary concerning the follow up period and provide a new diary for the second follow up period.
 
The Investigator will instruct the patient that during the follow up period (from week 13 to week 24) other topical treatments will be allowed at discretion of the treating physician. Such treatments will be recorded by the investigators.
 
The patient has to register the use other preservative free artificial tears in the patient's diary.

At home	Days 84 ± 4 – 168 ± 7	
 ➤ Recording any new or changes in concomitant medications (diary) ➤ Recording any unusual medical conditions - AE monitoring (diary) ➤ Artificial tears use during 4 weeks of FU (diary) 
Data will be recorded by the patient on the patient's diary.

	Day	Procedures/Assessments

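### The Protocol both bars and permits other topical eye treatment after week 12; this touches the descriptive week 16 assessments and deviation status, not the co-primary or key secondary tests

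*Protocol*

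**What the plan says.** **Text that bars other treatment.** Protocol 5.6 states, as a general rule, that "no ophthalmic medication other than study drug will be given to the patient from the screening day until all of the final study evaluations" are complete. Its one exception is preservative-free artificial tears supplied by the Sponsor. Protocol 6.1 says that from screening patients "will stop any kind of further ophthalmic treatment, until all of the final study evaluations have been completed, except preservative free artificial tears"; here the tears need not be the Sponsor's. Exclusion criterion 12 (synopsis and section 4) lists "Use of topical corticosteroids, lifitegrast, autologous serum tears in either eye during the study", with no end at week 12.

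**Text that permits it.** Protocol 3.3 says: "During the follow up period after week 12 until week 24 other topical treatments will be allowed at discretion of the treating physician". The synopsis says the same for weeks 13 to 24. At Visit 5 (week 12) the investigator is to give the patient this instruction: "during the follow up period (from week 13 to week 24) other topical treatments will be allowed at discretion of the treating physician". SAP 3.3 repeats the permission and mentions no ban.

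**Text with a narrower permission.** The opening of Protocol 6.2 says that after week 12 "patients can use others artificial tears different from the artificial tears provided by the Sponsor". It names no other topical treatment and does not say that tears are the only thing allowed.

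No passage says which text prevails.

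**The concern.** A site that works from section 5.6 would withhold, or record as a deviation, a topical treatment that a site working from section 3.3 or the Visit 5 instructions may give freely. Two things depend on this.

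1. **Conditions at week 16.** Schirmer I, NEI staining, TFBUT, SANDE and IDEEL are all secondary endpoints with a week 16 time point (Protocol 7.1.2). If sites follow different sections, that visit is measured under different background treatment.
2. **Deviation status.** The PP set leaves out patients with major protocol deviations, and its definition sets no time limit (Protocol 9.2, SAP 7.2.6). Use in week 14, say, is a deviation under one section and allowed under another. SAP 6.2 and 7.9 now plan a single lock at the end of the study, so events in weeks 13 to 24 will be known when the PP set is fixed. A patient could leave the PP analyses of the co-primary endpoints because of something that happened after both had been measured.

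**Working it through.** No statistical figure is at issue, so the check is a comparison of texts plus one piece of visit-window arithmetic.

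**Step 1. The rules side by side for weeks 13 to 24**

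| Source | Other topical treatment | Artificial tears not from the Sponsor |
|---|---|---|
| Protocol 5.6 | barred, as a general rule | barred, as a general rule |
| Protocol 6.1 | barred | allowed if preservative-free |
| Exclusion criterion 12 | named agents barred | not addressed |
| Synopsis, Protocol 3.3, Visit 5, SAP 3.3 | allowed at physician's discretion | not barred |
| Opening of Protocol 6.2 | not mentioned | allowed |

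The first two rows contradict the fourth on other topical treatment. Criterion 12 contradicts the fourth row for the agents it names, if its wording is read to cover the whole study. The last row conflicts with 5.6 on the source of the tears, but it is compatible with the fourth row and only narrower in scope.

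**Step 2. Can the timing remove the conflict?** The phrase about final evaluations has two plausible meanings: the last efficacy visit (week 16, day 112) or the last study visit (week 24, day 168). The permission starts after week 12 (day 84). Since 112 > 84 and 168 > 84, the ban and the permission overlap under either meaning.

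**Step 3. Length of the overlap before week 16 efficacy.** The windows are day 84 ± 4 for week 12 and day 112 ± 7 for week 16 (Protocol section 2, SAP 4.4).

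- Nominal: 112 − 84 = 28 days
- Shortest: (112 − 7) − (84 + 4) = 105 − 88 = 17 days
- Longest: (112 + 7) − (84 − 4) = 119 − 80 = 39 days

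**Step 4. Which analyses fall in the overlap?**

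- Co-primary endpoints: weeks 4 and 12. Outside.
- Key secondary hierarchy (Protocol 9.4.3.3, SAP 10.2.1 and 10.2.2): every listed test is at week 4, 8 or 12. Outside. The Protocol's mixed model for IDEEL includes week 16 as a visit, but the tests read from it are at weeks 12 and 4, and the SAP's tables for the IDEEL, NEI and TFBUT models run to week 12.
- Week 16 secondary endpoints: inside. SAP 3.2.2 words these objectives as superiority testing, but week 16 is outside the hierarchy and is analysed under SAP 10.2.3, which is descriptive.
- PP analyses of the co-primary endpoints (SAP 10.1.4): supportive. They are affected only if post-week-12 use is classed as a major deviation, which is decided case by case before unblinding (SAP 8.2).

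**Step 5. Would planned outputs show the use?** Partly. Post-week-12 treatments are recorded, and concomitant medications are tabulated and listed. However, SAP 8.6 does not split concomitant medication at week 12, SAP 9.3 pools artificial-tear use over the whole follow-up, and nothing links either to the week 16 results.

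**The case against.** The case on the other side is substantial. The restrictive wording looks like the weaker text. Section 5.6 presents its ban as general, and its schedule for artificial tears stops after the eight follow-up weeks. Section 6.1 is the screening section and its sentence carries a parenthesis about the wash-out; the parallel sentence in section 3.3 limits the stop to the 8 to 10 days before baseline. The permission is specific to the period, appears in four places, and is to be explained to each patient at week 12. Sites may therefore behave alike in practice.

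That makes wide divergence less likely, but it does not remove the conflict. Section 5.6 names its one exception, section 6.1 has no softening phrase, and both run to the final evaluations.

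Three further points stand:

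- A reader might infer three mutually incompatible rules. The documents do not support that. The opening of section 6.2 contains no restriction to tears only, and the Visit 5 table in the same section states the wider permission.
- A reader might infer a biased treatment comparison at week 16. Randomization is stratified by site and treatment is masked, so a site's reading of the rule falls on both arms. Differences between sites mainly add noise. A single permissive rule would also leave background treatment varying at week 16.
- A reader might infer that patients will drop out of the PP set. That would require use which the synopsis, section 3.3, Visit 5 and the SAP all permit to be judged a major deviation. It is possible, not established.

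**Conclusion.** The Protocol contradicts itself on topical eye treatment between week 12 and the end of the study: sections 5.6 and 6.1, and exclusion criterion 12 for the agents it names, stand against the synopsis, section 3.3, the Visit 5 instructions and SAP 3.3. The opening of section 6.2 adds a difference of scope.

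The consequence is modest. It reaches the conditions of the descriptive week 16 assessments, over about 28 days (17 to 39), and the deviation status of use after week 12, with a possible knock-on to the supportive PP analyses. The conflict spans weeks 13 to 24, but that is calendar coverage and not a measure of effect; the documents give no basis for estimating how many patients are involved.

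A reader might go further and see a threat to the trial's main conclusions. The documents do not support this: the FAS co-primary analyses and every test in the key secondary hierarchy use time points up to week 12. This rests on the mixed models being fitted up to week 12, as the SAP's table titles indicate, and on deviations being settled before unblinding, as SAP 8.2 states.

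**What to change.** 1. Reconcile the synopsis, exclusion criterion 12, sections 3.3, 5.6 and 6.1, both statements in section 6.2 (its opening and the Visit 5 instructions) and SAP 3.3, so that one rule covers weeks 13 to 24. Which rule that should be is for the sponsor and investigators; nothing here favours one.
2. State in the SAP, before unblinding, that deviations for the PP set are judged against the reconciled rule.
3. Present week 16 results alongside recorded topical treatment after week 12, for example the number of patients per arm who used such treatment between the week 12 and week 16 visits.

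The cost is a Protocol clarification, a short SAP addition and one extra summary from data already collected. Sample size, visits and the primary analysis do not change.
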